|-------------------------|------|--------------------------------------|-----------------|------|------------------------------------|-------------|---|
| Nariesty ²³ | 2009 | Open label (Follow up) | n=13 | 6-16 | 500 to 4,000 mg milk protein | 3-17 months | Ongoing milk intake demonstrated tolerance from 1000 to 16,000 mg (median 7000) with 33% tolerating 16,000 mg on OFC |
| Pajno ²⁴ | 2010 | Randomized, placebocontrolled | n=15 | 4-10 | 200 mL | 18 weeks | 67% tolerant to 200 mL cow's milk |
| Martorell ¹⁹ | 2011 | Randomized, placebocontrolled | n=30 | 2-3 | 200 mL | 1 year | 90% showing complete desensitization |
| Keet ¹⁸ | 2012 | Randomized, OIT vs SLIT | n=20 for OIT | 6-17 | 1000-2000 mg | 60 weeks | 70% of patients receiving OIT passed an 8g OFC. Only 40% passed OFC when treatment was discontinued for 6 weeks. |
| Wood ²⁷ | 2015 | Omalizumab DBPC, openlabel OIT | n= 57 | 7-32 | 3300 mg | 24 months | 80% desensitized to 10 g OFC, Sustained unresponsiveness in 42% after 8 week |

However, OIT studies to date have shown high rates of adverse reactions, ranging from mild, local symptoms, such as oral itching, to severe systemic symptoms, such as anaphylaxis.^{12,26} In 2011, Martorell et al conducted a 1 year milk OIT study in 2-3 year old children. While 90% were desensitized, 47% developed moderate reactions (rhinoconjunctivitis, wheezing, vomiting, urticaria) over the course of treatment.¹⁹ In 2012, we examined the safety and efficacy of OIT and SLIT (sublingual immunotherapy) for cow's milk allergy. The study reported reactions in 30% of doses with most confined to oral pruritus, but with more significant reactions with OIT compared to SLIT.¹⁸ In addition, 10-20% of subjects have dropped out of OIT trials due to adverse reactions, most commonly chronic abdominal pain.^{12,26}

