Many of the 25-50% of cow's milk allergic patients who do not tolerate heated milk have a very severe, persistent phenotype. These children have a high risk of reactions due to accidental exposures and a low likelihood of naturally outgrowing their allergy and therefore, would benefit greatly from a safe and effective form of treatment. Our hypothesis is that children with IgE mediated CMA who are reactive to baked milk can be desensitized to cow's milk protein via baked milk OIT, and that this approach will prove far safer than OIT using unheated milk. We propose to explore the efficacy and safety of baked milk OIT in a double-blind, placebo-controlled study in children with persistent CMA, focusing on the more allergic children who are 1) unable to tolerate baked milk even at small servings; 2) unlikely to naturally outgrow their milk allergy; and 3) more likely to have difficulty tolerating OIT with uncooked milk.

This approach has this far been attempted in one small study in Israel with 15 baked milk reactive patients.²⁸ The primary outcome was defined as attaining a maintenance baked milk dose of 1.3 grams per day without adverse reactions at 1 year of treatment. This study started with a baked milk dose of 25-120 mg. Only 3/14 (21%) patients tolerated the 1.3g goal dose. Eight did not complete the program because of IgE-mediated reactions and 3 did not complete it for other reasons.

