As mentioned previously, there has only been 1 prior study using baked milk OIT. Goldberg et al had a different primary outcome which was the goal of attaining a maintenance BM dose of 1.3g/day.²⁸ Only 21% reached that goal but as mentioned above, the study protocol was different than our study protocol.

Based on these prior studies, we would expect that at most 10% of subjects in the placebo arm and at least 60% of subjects in the treatment arm would tolerate 2 grams of unheated milk at the 1 year OFC. To achieve an alpha of 0.05 and a power of 0.8, 14 subjects are needed in each group. 15 participants per group would allow for a 7% drop out rate.

Statistical plan:

We will display summary statistics for each variable to keep track of missing data, and to be alerted to suspicious patterns in the data and outliers. We will initially focus on the primary aim of the study. We will examine adverse event endpoints to estimate 1) the risk associated with OIT and 2) compare the risks of OIT between the risks of adverse reactions in the placebo group. We will tabulate the total number of serious adverse events (SAE) for the active treatment study population and construct a 95% confidence interval for this total number of adverse events. We will also calculate the proportion of subjects who experienced an SAE along with the 95% CI. We will calculate the proportion of subjects who experienced an SAE and construct the 95% CI. We will compare the proportion of doses resulting in an SAE between groups using Fisher's exact test. We will compare the number of adverse events between groups using the Kruskall-Wallis test if the variances between the groups are similar.

In addition to efficacy endpoints, we will tabulate data and calculate the proportion of subjects who achieved a clinical response and construct 95% confidence intervals. We will do this for each time point being evaluated so that we have estimates of clinical response rates after completion of 1 year of OIT, after 2 years of OIT, and after 1 year of placebo.

We will also compare clinical response rates between the active treatment and placebo groups at the year 1 and year 2 OFCs. We will tabulate the clinical response rates by group for each time point and use a t-test for difference in proportions to test for statistical significances in response rates between groups.

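### The 7% drop-out allowance is unexplained and below the protocol's own 10-20%, so power of 0.8 is not assured at 20% loss, and the plan does not say how drop-outs are counted

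*Combined protocol and SAP*

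**What the plan says.** Section 7.c bases the sample size on clinical response, the main secondary outcome. It assumes a placebo response rate of 10% or less and, for active treatment, that "at least 60% of subjects in the treatment arm would tolerate 2 grams of unheated milk at the 1 year OFC". It then states: "To achieve an alpha of 0.05 and a power of 0.8, 14 subjects are needed in each group". The allowance for loss is one sentence: "15 participants per group would allow for a 7% drop out rate". No source or reason for 7% is given. The section does not say whether a child who stops treatment counts as a non-responder or leaves the denominator.

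Three places in the protocol (section 1, section 3 and section 8.a.i) give a higher figure for earlier trials: "10-20% of subjects have dropped out of OIT trials due to adverse reactions". Section 8.a.i adds that these risks are seen as a worst case, because fewer reactions are expected with heated milk. Section 3 describes the one earlier baked-milk OIT study, in which 3 of 14 reached the goal dose: "Eight did not complete the program because of IgE-mediated reactions and 3 did not complete it for other reasons". Sections 3 and 7.c point out that its protocol differed from this one.

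Section 4 (D, and item e on treatment failure and removal) discontinues treatment for failing 3 mg on the first day, for three consecutive failed escalations below 750 mg, or for not reaching 750 mg by week 44. Section 4.H gives children who stop early a discontinuation visit with an examination, a pregnancy test where applicable, and a diary and history review. It schedules no food challenge at that visit.

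**The concern.** The allowance lies below the whole range that the protocol reports, and that range covers losses from adverse reactions only. At 10% loss per child, the chance of more than one loss among 15 is 45%; at 20% it is 83%. The stated power could therefore rest on a loss rate that the trial is unlikely to achieve.

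How losses are counted matters as much as how many there are. A child who cannot tolerate dosing never reaches the year 1 challenge. If the response rate is taken among challenged children, such failures disappear from the active arm and the treatment looks better than it is. If they are kept as non-responders, the meaning of the planning rates (all randomised children, or completers) decides what power the trial has. The plan settles neither question.

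**Working it through.** **Inputs (section 7.c).** Placebo rate 0.10, active rate 0.60, alpha 0.05, power 0.80, equal groups. Sidedness is not stated; two-sided is assumed.

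**Reproducing the 14.** The pooled-variance formula without continuity correction, with mean rate 0.35, is

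n = [1.960 × √(2 × 0.35 × 0.65) + 0.842 × √(0.10 × 0.90 + 0.60 × 0.40)]² / 0.50²
= [1.960 × 0.6745 + 0.842 × 0.5745]² / 0.25 = 13.04, rounded up to 14.

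The plan's figure reproduces. The 7% is 1/15 = 6.7%, that is, one child per group.

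**Chance of more than one loss among 15.** 1 − P(0) − P(1) from the binomial is 0.451 at 10% loss and 0.833 at 20%.

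**Drop-outs excluded.** From the same formula, power = Φ[(0.50 − 1.960 × SE₀) / SE₁]. SE₀ is the pooled standard error and SE₁ the unpooled one. At 12 per arm, SE₀ = 0.1947 and SE₁ = 0.1658, so power = Φ(0.714) = 0.762. The last column is the exact binomial probability that the planned t-test rejects.

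| Evaluable (placebo / active) | Arises from | Pooled formula | Exact t-test |
|---|---|---|---|
| 15 / 15 | no loss | 0.858 | 0.877 |
| 14 / 14 | the plan's one loss per arm | 0.830 | 0.848 |
| 13 / 13 | 10% loss (13.5), rounded down | 0.799 | 0.835 |
| 12 / 12 | 20% loss in both arms | 0.762 | 0.791 |
| 15 / 12 | 20% loss in the active arm only | 0.816 | 0.860 |

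At 10% loss, 13 to 14 children per arm remain and power is 0.80-0.83.

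**All 15 per arm analysed, non-completers as non-responders.** The result depends on what the 60% and 10% mean.

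- If they already describe all randomised children, nothing changes: 0.858 pooled, 0.877 exact.
- If they describe completers, each affected rate is multiplied by (1 − loss):

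| Loss | Arms affected | Rates (active vs placebo) | Pooled formula | Exact t-test |
|---|---|---|---|---|
| 10% | both | 0.54 vs 0.09 | 0.786 | 0.822 |
| 10% | active only | 0.54 vs 0.10 | 0.760 | 0.795 |
| 20% | both | 0.48 vs 0.08 | 0.704 | 0.751 |
| 20% | active only | 0.48 vs 0.10 | 0.643 | 0.687 |

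**The case against.** The best defence is that the 7% is optimistic but not contradicted. Section 8.a.i treats the 10-20% as a worst case, the milk OIT studies tabulated in section 3 all used unheated milk, and the protocol explains why the earlier baked-milk study is a poor guide. This stands: a reader might infer that the protocol's own figures refute the 7%, but they only leave it unsupported.

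A second tempting inference is that power really is 0.69-0.75 (exact) at 20% loss. That requires the 60% to be a rate among completers. The presence of a drop-out allowance hints at this, but the text speaks of subjects in the treatment arm, and section 4, item e, lists the dosing failures under treatment failure. They can be read as already inside the 60%. Reducing 60% to 48% would then count the same failures twice, and power at 15 per arm would be 0.86-0.88.

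Third, with drop-outs excluded the loss of power is small. The planned t-test has exact power 0.79 at 12 per arm, and there is no shortfall if only the active arm loses children.

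Finally, response is a secondary outcome and the primary is safety. That is true, but this is the only calculation that supports the sample size. None of these arguments supplies a reason for 7% or says how drop-outs are counted.

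**Conclusion.** The point holds in a limited form. The base calculation is right. The allowance of one loss per group is unexplained and sits below the range that the protocol reports. By the formula that reproduces the 14, the stated 0.8 is essentially kept at 10% loss (0.80-0.83) and missed by about 4 points at 20% in both arms (0.76), or by about 1 point on the exact scale (0.79). This assumes two-sided testing and equal, excluded losses. The documents do not support calling the trial clearly underpowered, nor do they require more children.

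The more consequential gap is the undefined denominator. Until the plan says who is counted and what the 60% and 10% describe, power by the pooled formula at up to 20% loss could be anywhere from 0.64 to 0.86, and a rate among challenged children would favour the active arm.

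**What to change.** In section 7.c:

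1. Define the response-rate denominator as all randomised children, with non-completers counted as non-responders. State that this includes children who fail 3 mg on the dose escalation day: section 5 lists that as an exclusion, but it occurs after randomisation.
2. Say whether the 60% and 10% are rates among all randomised children or among completers.
3. Replace the 7% sentence with the power for 15 per group, by one named method. If the rates apply to all randomised children, this is 0.86 by the pooled formula (0.88 exact). If they apply to completers, it is 0.76-0.79 at 10% loss and 0.64-0.70 at 20% by the pooled formula (exact t-test 0.80-0.82 and 0.69-0.75).
4. Tie the restated power to a response that is measured at the year 1 challenge. The present calculation uses unheated milk at one year, but sections 4 (item 1) and 8.a.v provide only a baked-milk challenge then. If the endpoint changes to baked milk, the assumed rates need their own justification, and the figures in step 3 apply only if 60% and 10% are retained.

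The cost is one rewritten paragraph and possibly a less favourable stated power. No extra enrolment and no change to visits or treatment is needed.

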The study treatment is non-fat cow's milk powder or placebo ingested in a baked form. The non-fat cow's milk powder will be provided by the University of North Carolina (UNC). It is manufactured by The Milky Whey, Inc & TMW International. It will be refrigerated at the site at 2 through 8°C until provided to the participants. Detailed instructions will be provided regarding how the baking should be performed.

The doses chosen are based on prior milk OIT studies, which have all used unheated milk. We anticipate similar efficacy with greater safety using this approach.

b. Justification and safety information if FDA approved drugs will be administered for nonFDA approved indications or if doses or routes of administration or participant populations are changed.

Aside from the skin testing extracts, this study will not use any drugs, but rather foods commonly available in households, prepared using a standard oven. Most milk OIT studies to date have used unheated milk at maintenance doses ranging from 500- 4000 mg. As described in the background section, these have shown high rates of adverse reactions, ranging from mild, local symptoms, such as oral itching, to systemic allergic reactions.

Baking milk has been shown to modify the allergen and make it less allergenic and therefore less likely to induce adverse reactions. It has been shown that 50-75% of children with

CMA tolerate baked milk at full servings, such as a cupcake or muffin, and many are already incorporating these foods into their diet at home.¹³ However, the remaining 25-50% of children with CMA are not able to tolerate baked milk at standard doses. Our dosing regimen will start with extremely small doses of baked milk protein and gradual escalation.

We believe that the chemistry and manufacturing of the non-fat milk powder and Tapioca Flour does not present signals of potential human risk, beyond the inherent risk associated with the investigational treatment protocol. This milk powder has been approved by the Food & Drug administration for use in other clinical trials (IND: 77,468) and in our study (IND: 17114).

c. Justification and safety information if non-FDA approved drugs without an IND will be administered.

N/A

7. Study Statistics

a. Primary outcome variable.

The primary objective of this trial is to study the safety of baked milk OIT, defined as the incidence of adverse events on baked milk OIT compared to adverse events on placebo.

b. Secondary outcome variables.

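### The primary adverse-event contrast has no planned estimate or confidence interval: intervals cover serious events only, and the arms are compared only by significance tests.

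*Combined protocol and SAP*

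**What the plan says.** Section 7.a defines the primary outcome as safety, meaning "the incidence of adverse events on baked milk OIT compared to adverse events on placebo". Section 2 and the opening of Section 7.c say the same. The statistical plan in 7.c then undertakes to estimate the risk of oral immunotherapy (OIT) and to "compare the risks of OIT between the risks of adverse reactions in the placebo group". The analyses listed for this are:

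- the total number of SAEs in the active arm, with a 95% CI;
- the proportion of children with an SAE, with a 95% CI: "We will calculate the proportion of subjects who experienced an SAE and construct the 95% CI". The sentence before it says the same thing, and neither names an arm;
- Fisher's exact test between groups on the proportion of doses that led to an SAE;
- for all AEs: "We will compare the number of adverse events between groups using the Kruskall-Wallis test", on condition that the two groups have similar variances. No alternative is given if they do not.

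The sample size in 7.c rests on a secondary efficacy outcome, tolerance of 2 g of unheated milk, expected in "at most 10% of subjects in the placebo arm and at least 60% of subjects in the treatment arm".

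**The concern.** The primary outcome is a contrast in AE incidence, and the plan produces no number for that contrast. A significant rank test would show that the arms differ but not by how much. A non-significant one would come without a limit on the excess harm still compatible with the data. The sole comparison of all AEs also depends on a condition that a real treatment effect is likely to break, and then no primary comparison is left.

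The gap is confined to safety. For clinical response, the same section plans proportions with 95% CIs after one year of OIT, after two years of OIT and after one year of placebo.

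**Working it through.** **The plan's own figure.** Inputs from 7.c: 10% v 60%, alpha 0.05, power 0.80. Sidedness is not stated; two-sided is assumed. With the pooled formula and no continuity correction, mean proportion 0.35:

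n = [1.960 × √(2 × 0.35 × 0.65) + 0.842 × √(0.10 × 0.90 + 0.60 × 0.40)]² / 0.50² = 13.04, rounded up to 14.

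This agrees with "To achieve an alpha of 0.05 and a power of 0.8, 14 subjects are needed in each group". Fifteen per group allows for 1 - 14/15 = 6.7% loss, which matches "15 participants per group would allow for a 7% drop out rate". The figure reproduces, but it says nothing about AEs.

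**What is planned, by endpoint.**

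| | Estimate with CI | Between-arm contrast with CI | Between-arm test |
|---|---|---|---|
| All AEs (primary) | none | none | Kruskal-Wallis, conditional on variances |
| SAEs | active-arm total; proportion of children, arm not named | none | Fisher, by dose |

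**What 15 children per arm can exclude.** The documents give no expected AE rate for this trial, so the counts below are assumptions. The unit is the child, so these figures do not reproduce the planned dose-level Fisher test. The interval is Newcombe's, built from the Wilson limits (l, u) of each arm:

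lower = d - √[(p₁ - l₁)² + (u₂ - p₂)²], upper = d + √[(u₁ - p₁)² + (p₂ - l₂)²].

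- 0/15 v 0/15: Wilson upper limit = 3.84/(15 + 3.84) = 0.204 in each arm, so d = 0 with 95% CI -20 to +20 points; p = 1.
- 7/15 v 3/15: 7/15 is close to the 47% with moderate reactions that Section 8.a cites from an unheated-milk study; 3/15 is assumed. Wilson limits are 0.248 to 0.699 and 0.070 to 0.452, and d = 0.267.
  - Lower: 0.267 - √(0.219² + 0.252²) = -0.067.
  - Upper: 0.267 + √(0.232² + 0.130²) = +0.533.
  - The result is +27 points (-7 to +53), Fisher p = 0.25.

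**Power of the rank test on AE counts.** Simulated with 15 v 15, negative binomial counts, an assumed 3 or 10 AEs per placebo child, and dispersion k = 0.5, 1 or 2:

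| True rate ratio | Power across the six settings |
|---|---|
| 2 | about 16% to 61% |
| 5 | about 60% to 100% |
| 10 | about 84% to 100% |

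Repeat runs differ by a few points; the low end at a ratio of 5 came out between 57% and 60%. At a ratio of 2, one set of runs gave 0.17, 0.29 and 0.48 (mean 3) and 0.17, 0.35 and 0.59 (mean 10) for k = 0.5, 1 and 2, so five of the six settings are below one half.

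**The variance condition.** Under the same model the variance is m + m²/k. With m = 3 and k = 1 the placebo variance is 3 + 9 = 12. At a doubled rate the active variance is 6 + 36 = 42, which is 3.5 times as large. A real increase in AEs would therefore tend to breach the condition on which the only all-AE comparison depends.

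**The case against.** The plan is not empty on safety. It promises summary statistics for every variable, gives two SAE quantities a 95% CI, and cannot run Fisher's test without the SAE proportion of doses in each arm. A reader might infer that safety is reported by p-values alone; for SAEs the documents do not support that. But the summary statistics are meant for tracking missing data, odd patterns and outliers, and none of these items is an all-AE incidence or a contrast with an interval.

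A reader might also infer that a non-significant test is meant to pass as proof of safety. No passage says so, and Sections 1 and 3 speak of exploring safety. What can be said is that the plan gives no margin and no rule of interpretation, so that reading is not ruled out.

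The illustrations have limits too. The planned Fisher test counts doses. Assuming 15 × 365 = 5,475 daily doses per arm, 4 v 0 SAEs give p = 0.12. Counting doses treats repeated doses in one child as independent and supplies no estimate either. Low power of the rank test is specific to a modest rate ratio. Section 8.a cites reaction rates of 27% to 36% with unheated milk, which the protocol regards as a worst case. Even well below that, daily dosing could give a ratio far above 2, where the test would usually be significant. The missing size of effect would then be the main loss.

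The stopping rules and the data safety monitoring board protect participants but do not fill the reporting gap.

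**Conclusion.** The concern holds in this form: followed as written, 7.c gives no per-arm incidence for all AEs and no between-arm difference or ratio with a CI for AEs or SAEs. Its one all-AE comparison is a conditional test with no fallback. At 15 per arm, non-significant child-level results are compatible with an excess of about 20 points when no events occur, and of more than 50 points in the 7/15 v 3/15 example. These sizes rest on assumed counts, and the power figures on assumed means, dispersion and rate ratios. The finding about what is and is not planned rests on the text alone. The change should be made, but it does not call the design or the sample size arithmetic into question.

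**What to change.** In Section 7.c, replace the repeated SAE sentence. For the blinded year, by randomised arm, report:

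- the proportion of children with at least one AE, and with at least one SAE, with the risk difference (active minus placebo) and a 95% CI, for example Newcombe's;
- the AE rate per dose or per unit of time on treatment, with the active/placebo ratio and a 95% CI that treats the child as the unit (bootstrap over children, or a negative binomial model with an exposure offset).

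The exposure denominator is needed because Section 4 (D and e) stops treatment early for failed escalation or severe symptoms. Children on active treatment may thus have less time at risk, and AEs per child could understate the harm rate.

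Keep the rank test as a supporting p-value, without the equal-variance condition. State that a non-significant test will not be reported as showing no excess risk, and that the conclusion will quote the confidence limits. This is a reporting rule, not a decision rule. A decision rule would need an acceptable excess fixed in advance, and the documents give none.

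The cost is SAP wording and a few lines of analysis on data already collected, since the daily diaries record doses and events. No added children or visits are needed. The downside is that wide intervals will be shown, so the safety statement will read less favourably.
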